### 3.5.2 Selection of Endpoints

In the phase 3 trial ESTHER-1 it was demonstrated that individualised FE 999049 dosing based on the subjects AMH and body weight in comparison to conventional rFSH treatment increased the number of oocytes retrieved in subjects with low AMH ( $< 15$  pmol/L) and decreased the number of oocytes retrieved in subjects with high AMH ( $\geq 15$  pmol/L), the latter reducing the occurrence of preventive interventions for early OHSS.

The primary endpoint of this trial, the number of oocytes retrieved, is an endpoint reflecting the pharmacological effect of FSH on follicular development and growth, and it is associated with the risk of OHSS. Previous comparative trials with GnRH antagonist versus long GnRH agonist protocols, including meta-analyses, have demonstrated that following rFSH treatment in a GnRH antagonist protocol, less oocytes are retrieved and accordingly a lower risk of OHSS is observed.

The primary endpoint of this trial will allow the comparison of distribution of the number of oocytes retrieved following each GnRH analogue protocol, and more specifically in subjects with low AMH (<15 pmol/L) and high AMH ( $\geq 15$  pmol/L). Based on current knowledge about the difference in ovarian response following treatment with CHO-derived rFSH in either protocol an overall treatment difference of at least 1 oocyte is to be anticipated, the difference being smaller in subjects with low AMH than in subjects with high AMH. This treatment difference, especially in subjects with high AMH, will indicate whether the FE 999049 dosing algorithm remains safe and effective when applied in a GnRH agonist protocol.

Secondary endpoints include standard efficacy endpoints in fertility treatment such as pregnancy outcomes, e.g. clinical pregnancy rate and ongoing pregnancy rate. Cycle cancellation due to poor or excessive ovarian response, blastocyst transfer cancellation due to (risk of) OHSS, distribution of number of oocytes retrieved, total gonadotropin dose and number of stimulation days will also be assessed.

Secondary endpoints related to safety include adverse events, early OHSS and late OHSS. Technical malfunction of the pre-filled injection pen used for administration of FE 999049 will also be monitored.

Other secondary endpoints include pharmacodynamic parameters such as ovarian response in terms of follicular development, endocrine profile and also embryo and blastocyst quality. Follicular development will be evaluated on day 6 as well as at end-of-stimulation. The endocrine profile consists of FSH, LH, estradiol, progesterone, and inhibin B and will be evaluated on stimulation day 6, end-of-stimulation and at oocyte retrieval.

Post-trial activities cover follow-up of ongoing pregnancies up to live birth and neonatal health data at birth and at 4 weeks after birth. Neonatal health data will be gathered to provide additional safety information.

### **3.5.3 Blinding**

This trial is open label and unblinded due to the different protocols being compared and no measures are taken to prevent investigators, delegated trial staff or subjects from knowing the treatment allocation or dose of FE 999049 administered. It would be impractical to blind the protocols as they differ in respect to when treatment with GnRH agonist and GnRH antagonist, respectively, is initiated, and when the subject is to start stimulation with FE 999049.

### **3.5.4 Selection of Doses in the Trial**

#### **FE 999049**

Modelling and simulation based on the efficacy and safety data obtained in the European phase 2 trial (000009) have been used to identify the overall dosing regimen for FE 999049. The objective

of the FE 999049 dosing regimen is to obtain an appropriate ovarian response of 8-14 oocytes in most subjects, to minimise the proportion of subjects with <4 oocytes due to risk of unavailability of blastocysts for transfer, and to minimise the proportion of subjects with 15 oocytes or more as well as 20 oocytes or more due to the risk of early moderate/severe OHSS.

AMH and body weight were found to influence the dose-response with regard to obtaining the aim of the model of the FE 999049 dosing regimen. The impact of body weight on ovarian response is clinically relevant for low dose levels of FE 999049, while the effect is only minor at dose levels of 12 µg and above. The proposed individualised dosing regimen of FE 999049 is described in detail in section 5.1 and is summarised as follows: for subjects with AMH <15 pmol/L the daily FE 999049 dose is 12 µg, irrespective of body weight, and for subjects with AMH ≥15 pmol/L the daily FE 999049 dose is on a continuous scale ranging from 0.19 to 0.10 µg/kg, i.e. dependent on actual AMH and body weight. The safety and efficacy of this dosing regimen has been confirmed in the phase 3 trial ESTHER-1, and the dosing regimen of FE 999049 in this trial will be the same dosing regimen that was evaluated in the phase 3 trial and according to the labelling.

### **Concomitant Fertility Medication**

The doses and overall treatment regimens for the GnRH agonist (GONAPEPTYL), GnRH antagonist (CETROTIDE), hCG (OVITRELLE) and progesterone (LUTINUS) products are in line with the recommendations in the respective products' labelling for the indication of ART and/or standard clinical practice.

#### **3.5.5 Selection and Timing of Dose for Each Subject**

The proposed individualised dosing regimen of FE 999049 is described in detail in section 5.1.

#### **3.5.6 Selection of the Trial Population**

This trial applies similar inclusion/exclusion criteria as ESTHER-1 and will include women undergoing their first IVF/ICSI cycle, as this group of patients is considered the most appropriate population for a trial using different treatment protocols. The subjects have been diagnosed with tubal infertility, unexplained infertility, endometriosis stage I/II or have partners diagnosed with male factor infertility, and are considered eligible for IVF or ICSI. The trial will include women up to 40 years of age and will thereby cover the patient age span in which most ART treatments are performed. The allowed body mass index (BMI) is 17.5-32.0 kg/m^2, thus including underweight, normal weight, overweight and obese patients.

Subjects with an AMH level > 35 pmol/L at screening will be excluded from the trial as these subjects are likely to have polycystic ovaries and may have an increased risk of OHSS. Subjects with a strong preference for either treatment protocol will also be excluded from the trial. For example, some subjects may prefer the short term GnRH antagonist protocol or suffer from needle

fobia which could cause more premature discontinuations among subjects randomised to the GnRH agonist protocol. Furthermore, the exclusion criteria incorporate the contraindications for the use of gonadotropins.

Altogether, the population selected for this trial would be expected to be representative for patients undergoing controlled ovarian stimulation in IVF/ICSI cycles.

### **3.5.7 Withdrawal Criteria**

Description of specific withdrawal criteria for the individual subject is listed in section [4.4](#).

### **3.5.8 Follow-up Procedures**

#### **Post-trial Activities**

Post-trial activities includes follow-up of ongoing pregnancies and neonatal health follow-up at birth and at 4 weeks after birth.

#### **Safety Follow-up**

After the subject's last visit, the investigator must follow-up on any adverse event classified as serious or considered to have a reasonable possible causality to the investigational medicinal product (IMP) until it is resolved or until the medical condition of the subject is stable. All such relevant follow-up information must be reported to Ferring. If the event is a chronic condition, the investigator and Ferring may agree that further follow-up is not required.

#### **Access to Therapy after End-of-trial**

In December 2016, Ferring received Marketing Authorisation approval from the European Commission for FE 999049 and the product is approved under the trade name REKOVELLE in all countries included in this trial. Commercial availability may vary across countries.

## 4 SELECTION OF TRIAL POPULATION

### 4.1 Trial Population

#### 4.1.1 Inclusion Criteria

Subjects must meet all of the criteria listed below to be eligible for participation in the trial.

1. Informed Consent Forms signed prior to screening evaluations.
2. In good physical and mental health.
3. The subjects must be at least 18 years (including the 18th birthday) when they sign the Informed Consent Form and no more than 40 years (up to the day before the 41st birthday) at the time of randomisation.
4. Infertile women diagnosed with tubal infertility, unexplained infertility, endometriosis stage I/II or with partners diagnosed with male factor infertility, eligible for in vitro fertilisation (IVF) and/or intracytoplasmic sperm injection (ICSI) using fresh or frozen ejaculated sperm from male partner or sperm donor.
5. Infertility for at least one year before randomisation for subjects <38 years or for at least 6 months for subjects  $\geq 38$  years (not applicable in case of tubal or severe male factor infertility).
6. The trial cycle will be the subject's first controlled ovarian stimulation cycle for IVF/ICSI.
7. Regular menstrual cycles of 24-35 days (both inclusive), presumed to be ovulatory.
8. Hysterosalpingography, hysteroscopy, saline infusion sonography, or transvaginal ultrasound documenting a uterus consistent with expected normal function (e.g. no evidence of clinically interfering uterine fibroids defined as submucous or intramural fibroids larger than 3 cm in diameter, no polyps and no congenital structural abnormalities which are associated with a reduced chance of pregnancy) within 1 year prior to randomisation.
9. Transvaginal ultrasound documenting presence and adequate visualisation of both ovaries, without evidence of significant abnormality (e.g. no endometrioma greater than 2 cm or enlarged ovaries which would contraindicate the use of gonadotropins) and normal adnexa (e.g. no hydrosalpinx) within 1 year prior to randomisation. Both ovaries must be accessible for oocyte retrieval.
10. Early follicular phase (cycle day 2-5) serum levels of FSH between 1 and 15 IU/L at screening.
11. Negative serum Hepatitis B Surface Antigen (HBsAg), Hepatitis C Virus (HCV) and Human Immunodeficiency Virus (HIV) antibody tests within 1 year prior to randomisation.
12. Body mass index (BMI) between 17.5 and 32.0 kg/m^2 (both inclusive) at screening.
13. If  $< 38$  years willing to accept single blastocyst transfer. If  $\geq 38$  years willing to accept transfer of a single good-quality blastocyst (double blastocyst transfer may be performed if no good-quality blastocyst is available).

#### 4.1.2 Exclusion Criteria

Subjects meeting any of the criteria listed below will **not** be eligible for participation in the trial.

1. AMH >35 pmol/L at screening.
2. Strong preference of the subject for either treatment protocol.
3. Known endometriosis stage III-IV (defined by the revised ASRM classification, 1996).
4. Known history of recurrent miscarriage (defined as three consecutive losses after ultrasound confirmation of pregnancy (excl. ectopic pregnancy) and before week 24 of pregnancy).
5. Known abnormal karyotype of subject or of her partner / sperm donor, as applicable, depending on source of sperm used for insemination in this trial.
6. Any known clinically significant systemic disease (e.g. insulin-dependent diabetes).
7. Known inherited or acquired thrombophilia disease.
8. Active arterial or venous thromboembolism or severe thrombophlebitis, or a history of these events.
9. Known porphyria.
10. Any known endocrine or metabolic abnormalities (pituitary, adrenal, pancreas, liver or kidney) with the exception of controlled thyroid function disease.
11. Known tumours of the ovary, breast, uterus, adrenal gland, pituitary or hypothalamus which would contraindicate the use of gonadotropins.
12. Known moderate or severe impairment of renal or hepatic function.
13. Currently breast-feeding.
14. Undiagnosed vaginal bleeding.
15. Known abnormal cervical cytology of clinical significance observed within three years prior to randomisation (unless the clinical significance has been resolved).
16. Findings at the gynaecological examination at screening which preclude gonadotropin stimulation or are associated with a reduced chance of pregnancy, e.g. congenital uterine abnormalities or retained intrauterine device.
17. Pregnancy (negative pregnancy test must be documented at screening) or contraindication to pregnancy.
18. Known current active pelvic inflammatory disease.
19. Use of fertility modifiers during the last menstrual cycle before randomisation, including dehydroepiandrosterone (DHEA), metformin or cycle programming with oral contraceptives, progestogen or estrogen preparations.
20. Use of hormonal preparations (except for thyroid medication) during the last menstrual cycle before randomisation.
21. Known history of chemotherapy (except for gestational conditions) or radiotherapy.

22. Current or past (1 year prior to randomisation) abuse of alcohol or drugs and/or current (last month) intake of more than 14 units of alcohol per week.
23. Current or past (3 months prior to randomisation) smoking habit of more than 10 cigarettes per day.
24. Hypersensitivity to any active ingredient or excipients in the medicinal products used in the trial.
25. Previous participation in the trial.
26. Use of any non-registered investigational drugs during the last 3 months prior to randomisation.

## **4.2 Method of Assigning Subjects to Treatment Groups**

### **4.2.1 Recruitment**

The participating subjects will be recruited among the patients attending the clinics. Advertisements may be used if approved by the local ethics committee and regulatory authorities, as applicable according to local regulations.

A screening number is allocated to each subject who has given written informed consent to participate in the trial. A subject must always be assigned to the lowest available screening number at each site. A subject screening/enrollment log for all screened subjects must be maintained by the investigator.

### **4.2.2 Randomisation**

Randomisation may take place as soon as all eligibility criteria are met. Subjects will be randomised in a 1:1 ratio to controlled ovarian stimulation with FE 999049 in a long GnRH agonist protocol or to controlled ovarian stimulation with FE 999049 in a GnRH antagonist protocol.

Randomisation is performed centrally through the electronic case report form (e-CRF) and will be stratified by centre and according to age (<35, 35-37 and 38-40 years). The randomisation number will be allocated to the subject together with the treatment allocation. When a subject is randomised to the trial, she will always be assigned to the lowest available randomisation number. An independent statistician at the Ferring Global Biometrics Department will prepare a computer-generated randomisation list and randomisation is performed in blocks. Blocks will be maintained within centres, i.e. the randomisation will be stratified by centre. The block size will only be revealed when the trial database is declared clean and locked. An overview of recruitment will be recorded on a subject identification code list for all randomised subjects kept by the investigator.

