**Figure 3-2 Trial Diagram – Post-trial Activities**

### 3.1.2 Overall Design and Control Methods

#### Trial Design

This will be a randomised, controlled, open label, parallel group, multicentre trial comparing the efficacy and safety of individualised FE 999049 dosing in first cycle patients aged 18-40 years undergoing controlled ovarian stimulation for IVF/ICSI following either a long GnRH agonist protocol or a GnRH antagonist protocol. The trial has been designed to describe potential differences in the mean number of oocytes retrieved with adequate precision.

Subjects will be screened within 90 days prior to randomisation for compliance with the inclusion and exclusion criteria. Randomisation may take place as soon as all eligibility criteria are met. Randomisation does not necessarily need to take place at a physical visit, but can be done by delegated trial staff without the subject being present at the clinic. However, the subject will be contacted prior to randomisation to confirm eligibility. Subjects will be randomised in a 1:1 ratio to controlled ovarian stimulation with FE 999049 in a long GnRH agonist protocol or to controlled ovarian stimulation with FE 999049 in a GnRH antagonist protocol. Randomisation will be stratified by centre and according to age (<35, 35-37 and 38-40 years). The subject will be informed of treatment allocation and when to start treatment by the delegated trial staff.

Subjects randomised to treatment with FE 999049 in the long GnRH agonist protocol will start down-regulation with GnRH agonist (triptorelin acetate, GONAPEPTYL) 0.1 mg/day

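### If a single block size is used, as Protocol 4.2.2 reads, open-label sites could foresee roughly 10–30% of next assignments; block sizes should vary at random and be kept in a restricted document

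*Protocol*

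**What the plan says.** Protocol 4.2.2 sets a 1:1 ratio, performs randomisation centrally through the e-CRF, stratifies by centre and three age groups, and states that "randomisation is performed in blocks". It adds: "Blocks will be maintained within centres, i.e. the randomisation will be stratified by centre". On protecting the sequence it says only: "The block size will only be revealed when the trial database is declared clean and locked". The SAP says nothing about blocks.

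The trial is open label. Protocol 3.5.3 states that "no measures are taken to prevent investigators, delegated trial staff or subjects from knowing the treatment allocation". Under 4.2.2 the investigator also keeps a list of all randomised subjects.

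Three further provisions bear on the point:
- Protocol 3.1.2 says randomisation "can be done by delegated trial staff without the subject being present at the clinic".
- Protocol 6.2 lets it happen at any time once eligibility is met, up to 90 days from the screening visit.
- Exclusion criterion 2 in Protocol 4.1.2 is "Strong preference of the subject for either treatment protocol", which is judged before allocation.

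**The concern.** When allocation cannot be masked, selection at entry is prevented mainly by keeping the next assignment unpredictable. Central release hides the list but not the pattern of past allocations, which each site sees in full. With one block size, returns to balance within a stratum gradually rule out the alternatives. Once the size is known, an assignment is certain whenever one arm of the current block is full.

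Staff who foresee an assignment could bring a woman forward, hold her back, or apply the preference criterion more or less strictly. Her AMH result must be available before randomisation (Protocol 6.2), so they have some idea of her likely response. The primary model (Protocol 9.6.2, SAP 10.2) adjusts for age stratum and for AMH as below 15 or at least 15 pmol/L. AMH differences within those categories and clinical impressions stay unadjusted. Any resulting bias would enter the oocyte difference, which is the trial's main product, and the confidence interval would not show it.

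**Working it through.** **The plan's own figure.** Protocol 9.1 assumes SD 7.0 and 200 women per group. Half-width = 1.96 × 7.0 × √(2/200) = 1.37, stated as 1.4. It reproduces.

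**Stratum size.** Protocol 3.2 plans about 400 women at about 15 sites. 400/15 = 26.7 per site. Over three age groups, 400/45 = 8.9 per stratum. Equal recruitment is assumed, and strata of 9 are used below.

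**Size fixed and known from the start.** In a complete block of size b, the expected share of certain assignments is 1/(b/2 + 1): 50% (size 2), 33.3% (4), 25% (6), 20% (8). The last block in a stratum of 9 is incomplete, so:
- size 4: two complete blocks give 2 × 4/3 = 2.67 certain assignments; 2.67/9 = 29.6%, or 119 of 400
- size 6: one complete block gives 6/4 = 1.5; 1.5/9 = 16.7%, or 67 of 400
- size 8: one complete block gives 8/5 = 1.6; 1.6/9 = 17.8%, or 71 of 400

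**Size fixed but unknown.** The block size is not given, so sizes 4, 6 and 8 were each simulated (2,000 sites per setting). The observer sees only its own site's allocations by stratum and starts with equal weight on sizes 2, 4, 6 and 8. Shares are over the site's whole recruitment.

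| True size | Site (women per stratum) | Best guess of size right at the end | Next assignment predictable at ≥90% | Strictly certain |
|---|---|---|---|---|
| 4 | average (9+9+9) | 91% | 19% | 11% |
| 6 | average | 95% | 9% | 1% |
| 8 | average | 74% | 19% | 16% |
| 4 | large (40+24+16) | >99% | 30% | 14% |
| 6 | large | >99% | 20% | 17% |
| 8 | large | >99% | 21% | 19% |

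Hence roughly 10–30%. For size 4 at an average site, the best guess is usually right but its probability never reached 90%, so inference there is likely rather than assured. The size-8 results depend on 8 being the largest candidate.

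**Effect on the oocyte difference.** Let f be the fraction of sites that steer, all in the same direction. Let c be the share of assignments they act on, and Δ the contrast in expected yield between women steered to one arm and women steered to the other. The shift is f × c × Δ. The documents give neither f nor Δ, so f = 0.25 and Δ = 1 to 2 oocytes are assumptions.
- Lower: 0.25 × 0.11 × 1 = 0.03 oocytes (size 4, average site inferring the size)
- Upper: 0.25 × 0.296 × 2 = 0.15 oocytes (size 4, known throughout)
- Size 6 at an average site, strictly certain assignments only: 0.25 × 0.014 × 2 = 0.007, below this range

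Against the half-width, 0.03/1.37 = 2% and 0.15/1.37 = 11%.

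**With varying sizes.** In strata of 9, for an observer who knows which sizes are possible, certain assignments fall to 5.9% (sizes 4 and 6 mixed) or 2.6% (4, 6 and 8 mixed). Best-guess accuracy is 68.5%, 64.4% and 64.8% for fixed, known sizes 4, 6 and 8, against 65.1% for the 4/6/8 mix.

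**The case against.** The strongest objection is that a single size is nowhere stated. It is inferred from a singular noun, and a sponsor that varies its blocks has good reason to say little in a protocol that sites hold. That stands: the point is conditional. It does not remove the point, because the sentence reads most naturally as one size and nothing in either document contradicts that reading.

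A reader might infer that sites would know about 30% of assignments with certainty. That needs size 4 known from the first woman. An average site that has to infer the size reaches 11% strictly certain for size 4 and 1% for size 6.

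A reader might also infer a shift of over half an oocyte: 1 × 0.296 × 2 = 0.59. That needs every site to steer in the same direction, to know the size throughout, and to foresee a 2-oocyte contrast beyond what the model adjusts for. Nothing in the documents supports this, and opposed preferences would cancel.

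Existing controls count too. Allocation is released together with the randomisation number (4.2.2), all criteria must be met first (6.3), the woman is contacted beforehand (3.1.2), and all screened women are logged (4.2.1). Age group cannot be used to steer, and the AMH category is in the model. The preference in exclusion 2 is the subject's, not the staff's. These controls narrow the scope for steering, but none of them stops prediction or a choice of when to randomise.

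**Conclusion.** The point holds as a conditional and modest one. If one block size is used within centre-by-age strata, open-label sites can probably infer it and foresee roughly 10–30% of next assignments with full or at least 90% certainty. The plausible shift in the primary difference is about 0.03–0.15 oocytes if a quarter of sites steer. That is small beside the half-width of 1.4 and the anticipated difference of at least 1 oocyte (Protocol 3.5.2), but the interval does not include it.

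This rests on equal recruitment over 15 sites and three age groups, candidate sizes of 2 to 8, sites that track allocations by stratum, and the assumed steering fraction and contrast. The documents do not show that the size is fixed, that any site steered, or that the estimate is biased. The precision statement is unaffected. The case for change is that a better method is available at little cost.

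**What to change.** 1. Generate the list, or its unused part, with block sizes that vary at random within each centre-by-age stratum. Specify the sizes only in a restricted randomisation document. Naming them in the protocol would disclose them to sites.
2. In the Protocol 4.2.2 sentence on disclosure, replace the opening reference to a single block size with *Details of the blocking*, and leave the rest of the sentence as it is. If sizes already vary, this is the only change needed to the randomisation.
3. Extend the by-site summary in Protocol 9.5.1 and SAP 8.1 to show baseline balance between arms, including AMH. With about 13 women per arm per site (26.7/2), only gross imbalance would show, so it is a descriptive check.

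Cost: no extra subjects or visits, and slightly more arm imbalance in small strata. The SAP is based on a protocol version dated December 2020, while Protocol 3.1.3 plans first visits from Q1 2019 to Q3 2021. If recruitment is under way, the change needs an amendment and a list update in the e-CRF, and helps only women not yet randomised. Varying the sizes removes most certain predictions but barely lowers best-guess accuracy (about 65%), and not at all if the present size is 6 or 8.
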